Rationale	
In late 2019, a novel coronavirus was identified as the cause of a cluster of pneumonia cases in the city of Wuhan, China. This virus has now been designated severe acute respiratory syndrome coronavirus 2 (SARS-CoV-2), and the disease has been named COVID-19. To date, COVID-19 has affected >1,000,000 individuals across 204 countries and led to ~50,000 deaths. United States currently has the world's highest number of affected individuals with COVID-19 in the world, with >200,000 cases and >5,000 fatalities. The disease spectrum from COVID-19 varies within individuals and can broadly be categorized into three subsets: 1) mild upper respiratory tract illness in ~80%, 2) severe pneumonia requiring hospitalization in ~15%, and 3) critical illness with multiorgan dysfunction in ~5% of the patients. The overall fatality rate from COVID-19 is estimated at ~2%. A number of different investigational agents have been prescribed to patients with COVID-19; these agents can broadly be classified into two subgroups: 1) drugs aimed at inhibiting the viral growth such as the antiviral agents remdesivir and lopinavir-ritonavir, and hydroxychloroquine (either alone or in combination with azithromycin) and 2) drugs such as the IL-6 inhibitor tocilizumab, that are aimed at dampening the cytokine storm that is prevalent in critically ill patients with COVID-19. However, there is no proven effective pharmacological therapy against COVID-19 and supportive care remains the cornerstone of management. Development of novel treatment options for COVID-19 is a critical public health need.
 
A variety of laboratory parameters have emerged as prognostic biomarkers in patients with COVID-19 that can portend an increased propensity to progress towards acute respiratory distress syndrome (ARDS) and death. Key prognostic biomarkers reported thus far include elevated serum levels of ferritin, d-dimer, LDH, and lymphopenia. Lymphopenia has been observed in 60-80% of the hospitalized COVID-19 patients. Absolute lymphocyte count is inversely proportional to disease severity in patients with COVID-19 and patients with worse lymphopenia have increased risk of progression to ARDS and death. Lymphopenia was also seen in 50-80% of cases and predicted poor prognosis in patients with severe acute respiratory syndrome (SARS), a similar illness to COVID-19 that also assumed epidemic proportions and was caused by a related coronavirus, SARS-CoV. Analysis of blood and autopsy specimens from SARS patients revealed the presence of viral particles within circulating and tissue resident lymphocytes, thus implicating direct viral damage as the mechanism for the observed lymphopenia. T-lymphocytes have been demonstrated to play a crucial role in viral clearance in SARS, and play a key role in inhibiting the hyperactivation of innate immunity. A recent single cell transcriptome analysis performed on bronchoalveolar lavage fluid specimens obtained from six hospitalized individuals with COVID-19 revealed that patients with mild disease


	
had a more robust CD8 T cell adaptive immune response compared to patients with severe disease.
 
Sirolimus (rapamycin) is a macrolide produced by Streptomyces hygroscopicus that complexes with FKBP-12 and binds to and inhibits the mechanistic target of rapamycin (mTOR) pathway. Sirolimus is primarily used as an immunosuppressive agent to prevent rejection in organ transplant recipients. However, in contrast to its role as an immunosuppressive agent in the renal transplant population, sirolimus has been demonstrated to exert an immunostimulatory effect on CD8 T lymphocytes in response to viral infections. In addition, sirolimus has been shown to have an inhibitory effect on the replication of a variety of different viral pathogens, including a related coronavirus, MERS-CoV. In a single center trial, the addition of sirolimus to standard of care treatment resulted in faster viral clearance and improved oxygenation in critically ill patients with H1N1 influenza. Inhibiting the mTOR pathway has been shown to reduce mortality in a murine influenza model, upregulate antiviral gene expression, and boost the response to influenza vaccination in elderly patients. Lastly, a recently conducted pharmacology network analysis has suggested mTOR inhibition as a potentially useful strategy in patients infected with SARS-CoV-2.

Clinical Phase	II
Principal Investigator	[name], University of Cincinnati, Cincinnati OH
Participating Site(s)	University of Cincinnati - Cincinnati, OH
Accrual Objective	30 subjects
Study Objectives	The main objective of our study is to determine if treatment with sirolimus can improve clinical outcomes in hospitalized patients with COVID-19. Based on the results of this trial, additional phase III clinical development trials may be designed.
Study Design	Randomized, double blind, placebo-controlled study design
Dose and Duration of study drug	Sirolimus will be given as a 6mg oral loading dose on day 1 followed by 2mg daily for a maximum treatment duration of 14 days or until hospital discharge, whichever happens sooner.
Primary endpoint	Progression to respiratory failure requiring advanced support measures, either due to inadequate ventilation (non-invasive or invasive mechanical ventilation) or inadequate oxygenation (CPAP* or high flow supplemental oxygen at rates ≥ 15 liters/minute), in patients given sirolimus compared to the placebo group. * CPAP use for known obstructive sleep apnea will not be considered as disease progression.
Secondary endpoints	
Key secondary endpoints:
 
 • Escalation in level of care • Increase in total lymphocyte count

	
 Normalization of biomarkers (Ferritin, LDH, and d-dimer) Survival to hospital discharge Drug safety profile (Incidence and type of adverse and serious adverse events) 
Other outcomes measures:
 
 Fever Duration of advanced respiratory support Duration of hospital stay (in survivors) Time from treatment initiation to death (in non-survivors) Need for initiation of other off-label rescue therapies such as Anti IL-6 agents, at the discretion of treating clinicians
Inclusion Criteria	
Subjects enrolled in the trial must meet all of the following criteria.
 
 Confirmed COVID-19 pneumonia Hypoxia as defined by room air oxygen saturation less than 92% or supplemental oxygen requirement Presence of at least one additional biomarker that has been shown to predict poor prognosis: a) serum ferritin $\geq 500\text{ug/l}$, b) LDH $\geq 250\text{U/L}$, c) d-dimer $\geq 1\text{ug/L}$, or d) lymphopenia as defined by absolute lymphocyte count $<1,000/\text{uL}$ Age ≥ 18 years Completed informed consent
Exclusion Criteria	
Subjects who meet ANY of the following criteria are not eligible for enrollment as study participants:
 
 Known allergy or hypersensitivity to sirolimus Inability or refusal to provide informed consent Advanced respiratory support (high flow oxygen ≥ 15 L/min, CPAP, non-invasive or invasive mechanical ventilation) Active enrollment in other interventional clinical drug trials. Co-enrollment in observational studies and biorepositories is allowed. Pregnant women Breast feeding On chronic immunosuppression for other medical conditions such as rheumatological disorders, inflammatory bowel disease, or in patients with organ transplants. A list of these medications is provided in Section 12.3.4 Any clinically significant medical disease which in the opinion of the investigator precludes the patient from enrolling in the trial, including (but not limited to): 
 History of liver cirrhosis End stage renal disease or need for renal replacement therapy Decompensated heart failure Known active tuberculosis or history of incompletely treated tuberculosis Uncontrolled systemic bacterial or fungal infections Active viral infection other than COVID-19

	
 ○ Lymphoma or other systemic malignancies, either current or treated within the past 2 years. Localized non-melanoma skin cancer is not an exclusion.
Study Overview	
The main objective of our study is to determine if treatment with sirolimus can improve clinical outcomes in hospitalized patients with COVID-19. We will employ a randomized, double blind, placebo-controlled study design. 30 subjects will be randomized in a 2:1 fashion to receive sirolimus or placebo. Sirolimus will be given as a 6mg oral loading dose on day 1 followed by 2mg daily for a maximum treatment duration of 14 days or until hospital discharge, whichever happens sooner. Chart reviews will be conducted daily to determine changes in clinical status, concomitant medications and laboratory parameters. Study specific biomarkers will be measured at baseline and then at days 3, 7 and 14.

Sample Size	
In a study evaluating 201 hospitalized patients with COVID-19 in China, 82% (165 patients) required supplemental oxygen. Among the patients needing supplemental oxygen, 40% (67 patients) progressed to require advanced respiratory support during their hospital stay. Considering the fact that our study inclusion criteria mandates the need for supplemental oxygen and the presence of at least one additional poor prognostic biomarker, we anticipate that 50% of our control group will progress to require advanced respiratory support during their hospitalization. We expect that treatment with sirolimus will reduce the need for advanced respiratory support to 25%.
 
The goal of this pilot study is to determine a meaningful treatment difference in order to conduct a larger confirmatory trial. Given the limited data on treatment responsiveness in COVID-19 populations, we examined various enrollment sizes commensurate with planning a pilot study. Specifically, we undertook a recommended approach for pilot studies in clinical research, which is to not perform hypothesis testing with a significance level set at the traditional value of 0.05. The confidence intervals for the treatment difference were calculated based on demonstrating a reduction in the proportion of subjects needing advanced respiratory support from 0.50 in the placebo group to 0.25 in the sirolimus group. Various levels have been proposed as optimal thresholds for the tolerance of type I error in the context of pilot studies, with the highest being $p=0.25$. We chose the type I error rate of 0.2 to denote significant treatment effect between the treatment and placebo arms in our study, as proposed by Stallard. A sample size of 30 patients randomized in a 2:1 fashion in favor of sirolimus will allow us to estimate the treatment differences with 80% confidence based on a binomial two-proportion test. A two-sided test will be used since we are unsure if the treatment will have a beneficial effect in this patient population.

Data Analysis	
The primary endpoint of this study is progression to respiratory failure requiring advanced support measures. The difference in proportions of progression between the placebo and sirolimus groups and the 80% confidence interval will be calculated. If the confidence interval for the difference in proportions does not include zero, then we will conclude that the treatment difference is clinically meaningful. Considering the small sample size of our study, the significant impact of age and other pre-existing conditions such as diabetes mellitus on overall prognosis in patients with COVID-19 cannot be accounted for in the primary analysis. Patients will be randomized according to a computer-generated

permuted block randomization stratified on age: <50 years, 50 - 64 years, and ≥ 65 years. In case recruitment lags we will add external study sites. In such a scenario, University of Cincinnati and the facilities of the affiliated health systems UC Health, LLC and University of Cincinnati Physicians Company, LLC will follow the same randomization scheme. In case of other external sites, randomization will be stratified based on site in addition to the above-mentioned age-based stratification. As exploratory analysis, we will conduct analyses examining differences based on other prognostic factors, and concomitant medication use, such as corticosteroids, hydroxychlororquine, azithromycin etc. An intent-to-treat analysis will be performed for the primary outcome.

Table of Contents

1. Participating Institutions/Investigators Table (contact information).....	9
2. Glossary of Abbreviations	10
3. Background and Rationale	12
3.1 Background:	12
3.2 Lymphopenia and other poor prognostic biomarkers in COVID-19	12
3.3 T lymphocytes play a critical role in viral clearance in patients with SARS as well as COVID-19	12
3.4 Sirolimus is effective against a variety of viral pathogens including influenza as well as related coronaviruses	13
3.5 Rationale for the proposed study	13
4. Study Objectives and Endpoints	14
4.1 Main Study Objective	14
4.2 Primary Endpoint:	14
4.3 Secondary Endpoints:	14
5. Study Design.....	15
5.1 Identification and Screening	15
5.2 Inclusion Criteria	15
5.3 Exclusion Criteria	15
5.4 Recruitment.....	16
5.5 Study Drug Treatment.....	16
5.6 Treatment Regimen	17
6. Study Procedures and Timelines	18
6.1 Study and Timeline Overview.....	18
6.2 Schedule of Events	19
6.3 Study Visits	20
6.4 Enrollment.....	22

LAR	Legally authorized representative
LDH	Lactate dehydrogenase
MAR	Medication administration record
MERS	Middle East respiratory syndrome
mTOR	Mechanistic Target of Rapamycin
NCI	National Cancer Institute
NIH	National Institutes of Health
OHRP	Office for Human Research Protection
PPE	Personal protective equipment
PI	Principal Investigator
REDCap	Research Electronic Data Capture
SAE	Serious Adverse Event
SAR	Suspected Adverse Reaction
SARS	Severe acute respiratory syndrome
SARS-CoV-2	Severe acute respiratory syndrome coronavirus 2
SUSAR	Suspected, Unexpected Adverse Reaction
T_{max}	Median time to achieve peak plasma concentration
UC	University of Cincinnati
WBC	White blood cell

3. Background and Rationale

3.1 Background:

In late 2019, a novel coronavirus was identified as the cause of a cluster of pneumonia cases in the city of Wuhan, China. This virus has now been designated severe acute respiratory syndrome coronavirus 2 (SARS-CoV-2), and the disease has been named COVID-19. To date, COVID-19 has affected >1,000,000 individuals across 204 countries and led to ~50,000 deaths. United States currently has the world's highest number of affected individuals with COVID-19 in the world, with >200,000 cases and >5,000 fatalities.¹ The disease spectrum from COVID-19 is variable and can broadly be categorized into three subsets: 1) mild illness in ~80%, 2) severe pneumonia requiring hospitalization in ~15%, and 3) critical illness with multiorgan dysfunction in ~5% of the patients. The overall fatality rate from COVID-19 is estimated at ~2%.² A number of different investigational agents have been prescribed to patients with COVID-19; these agents can broadly be classified into two subgroups: 1) drugs aimed at inhibiting the viral growth such as the antiviral agents remdesivir³ and lopinavir-ritonavir⁴, and hydroxychloroquine (either alone or in combination with azithromycin)⁵ and 2) drugs such as the IL-6 inhibitor tocilizumab,⁶ that are aimed at dampening the cytokine storm that is prevalent in critically ill patients with COVID-19. However, there is no proven effective pharmacological therapy against COVID-19 and development of novel treatment options for COVID-19 is a critical public health need.

3.2 Lymphopenia and other poor prognostic biomarkers in COVID-19

A variety of laboratory parameters have emerged as prognostic biomarkers in patients with COVID-19 that can portend an increased propensity to progress towards acute respiratory distress syndrome (ARDS) and death. Key prognostic biomarkers reported thus far include elevated serum levels of ferritin, d-dimer, LDH, and lymphopenia.^{7,8} Lymphopenia has been observed in 60-80% of the hospitalized COVID-19 patients.⁸⁻¹¹ Absolute lymphocyte count is inversely proportional to disease severity in patients with COVID-19 and patients with worse lymphopenia have increased risk of progression to ARDS and death.^{7,8}

3.3 T lymphocytes play a critical role in viral clearance in patients with SARS as well as COVID-19

Lymphopenia was also seen in 50-80% of cases and predicted poor prognosis in patients with severe acute respiratory syndrome (SARS),^{12,13} a similar illness to COVID-19 that also assumed epidemic proportions and was caused by a related coronavirus, SARS-CoV. Analysis of blood and autopsy specimens from SARS patients revealed the presence of viral particles within circulating and tissue resident lymphocytes, thus implicating direct viral damage as the mechanism for the observed lymphopenia.¹⁴ T-lymphocytes have been demonstrated to play a crucial role in viral clearance in SARS,¹⁵ and play a key role in inhibiting the hyper-activation of innate immunity.¹⁶ A recent single cell transcriptome analysis performed on bronchoalveolar lavage fluid specimens obtained from six hospitalized individuals with COVID-19 revealed that

patients with mild disease had a more robust CD8 T cell adaptive immune response compared to patients with severe disease.¹⁷

3.4 Sirolimus is effective against a variety of viral pathogens including influenza as well as related coronaviruses

Sirolimus is a macrolide produced by *Streptomyces hygroscopicus* that complexes with FKBP-12 and inhibits the mechanistic target of rapamycin (mTOR) pathway. Sirolimus is primarily used as an immunosuppressive agent to prevent rejection in organ transplant recipients.¹⁸ However, in contrast to its role as an immunosuppressive agent in the renal transplant population, sirolimus has been demonstrated to exert an immunostimulatory effect on CD8 T lymphocytes in response to viral infections.¹⁹ In addition, sirolimus has been shown to have an inhibitory effect on replication of a variety of viral pathogens, including a related coronavirus, MERS-CoV.²⁰⁻²³ In a single center trial, the addition of sirolimus to standard of care resulted in faster viral clearance and improved oxygenation in critically ill patients with H1N1 influenza.²⁴ Inhibiting the mTOR pathway has been shown to reduce mortality in a murine influenza model,²⁵ upregulate antiviral gene expression, and boost the response to influenza vaccination in elderly patients.²⁶ Lastly, a recently conducted network analysis has suggested mTOR inhibition as a potentially useful strategy in patients infected with SARS-CoV-2.²⁷

3.5 Rationale for the proposed study

Improved understanding of the role of host immune response to SARS-CoV-2 infection and development of novel treatment options for COVID-19 are critical unmet public health needs. By harnessing the similarities between SARS-CoV-2 and SARS-CoV, and utilizing the insights gained from SARS, we believe that the key to successful recovery from COVID-19 lies in targeted stimulation of the host adaptive immune response. The mTOR inhibitor, sirolimus, has been shown to exert an immunostimulatory effect on CD8 lymphocytes in response to a variety of different viral pathogens, including a related novel coronavirus, MERS-CoV. We postulate that impaired T cell responsiveness is a key driver in the pathogenesis of severe COVID-19 and that treatment with sirolimus can enhance the virus-specific T cell response leading to effective viral clearance and improved clinical outcomes in patients with COVID-19. Sirolimus also inhibits viral replication by limiting cellular proliferation and progression through the cell cycle. Successful completion of our aims will lead to improved understanding of the role of adaptive immune response in mitigating COVID-19 pathology, and pave the way for the development of a novel treatment option for patients with COVID-19.

4. Study Objectives and Endpoints

4.1 Main Study Objective

The main objective of our study is to determine if treatment with sirolimus can improve clinical outcomes in hospitalized patients with COVID-19.

4.2 Primary Endpoint:

Progression to respiratory failure requiring advanced support measures, either due to inadequate ventilation (non-invasive or invasive mechanical ventilation) or inadequate oxygenation (CPAP* or high flow supplemental oxygen at rates \geq 15 liters/minute), in patients given sirolimus compared to the placebo group.

4.3 Secondary Endpoints:

Key secondary endpoints:

- Escalation in level of care
- Increase in total lymphocyte count
- Normalization of biomarkers (Ferritin, LDH, and d-dimer)
- Survival to hospital discharge
- Drug safety profile (Incidence and type of adverse and serious adverse events)

Other outcomes measures:

- Fever
- Duration of advanced respiratory support
- Duration of hospital stay (in survivors)
- Time from treatment initiation to death (in non-survivors)
- Need for initiation of other off-label rescue therapies such as Anti IL-6 agents, at the discretion of treating clinicians

* CPAP use for known obstructive sleep apnea will not be considered as disease progression.

5. Study Design

We will employ a randomized, double blind, placebo-controlled study design. 30 patients hospitalized with COVID-19 and meeting the inclusion criteria specified below will be randomized to receive sirolimus or placebo in a 2:1 manner. The treatment regimen and duration are provided in Sections 5.5 and 5.6.

5.1 Identification and Screening

Patients will be identified by the medical staff that cares for patients with COVID-19 at the University of Cincinnati Medical Center and the facilities of the affiliated health systems UC Health, LLC and University of Cincinnati Physicians Company, LLC. In addition, the study staff will actively screen for potential subjects by chart reviews of the patients admitted on the COVID units and based on automated alerts generated on patients under investigation for COVID-19. Identification and screening will take place until 30 evaluable patients have been enrolled, or the incidence of new cases does not permit further enrollment. Potentially eligible patients will be approached by the study investigators, and then by study staff. In order to limit staff exposure to patients with COVID-19 as well as to protect critical personal protective equipment (PPE), study investigators will communicate with potential subjects remotely via telephone rather than in-person visits, as much as possible. Potential patients will be informed about the study, and following completion of the informed consent process, a screening evaluation will be performed. The patient will provide informed consent before any study procedures are performed. Patients who learn of the study from the study listing on ClinicalTrials.gov or from any other source will also be able to be screened for enrollment.

5.2 Inclusion Criteria

Subjects enrolled in the trial must meet **all** of the following criteria.

- Confirmed COVID-19 pneumonia
- Hypoxia as defined by room air oxygen saturation less than 92% or supplemental oxygen requirement
- Presence of at least one additional biomarker that has been shown to predict poor prognosis: a) serum ferritin $\geq 500\text{ug/l}$, b) LDH $\geq 250\text{U/L}$, c) d-dimer $\geq 1\text{ug/L}$, or d) lymphopenia as defined by absolute lymphocyte count $<1,000/\text{uL}$
- Age ≥ 18 years
- Completed informed consent

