6.1 Study and Timeline Overview

Patients will be identified by the medical and research staff at the University of Cincinnati Medical Center and the facilities of the affiliated health systems UC Health, LLC and University of Cincinnati Physicians Company, LLC. Recruitment will take place until 30 evaluable patients have been enrolled, or the incidence of new cases does not permit further enrollment. Patients who meet eligibility criteria, provide informed consent and are enrolled in the study will receive instructions regarding study drug dosage, route and administration. The study drug will be given each morning along with other inpatient medications at roughly the same time every day. Patients will be on the study drug for a maximum duration of 14 days, or until hospital discharge, whatever happens first. In case a patient progresses to require advanced respiratory support, the study drug can continue as scheduled at the discretion of the treating clinician(s). If deemed clinically necessary on a case-by-case basis, in these scenarios the patient may need to be withdrawn ± unblinded.

All study procedures will take place after obtaining informed consent. Details of the informed consent process are provided in Section 6.3. Prior to starting study drug, baseline demographic and clinical variables will be collected along with vital signs, amount of supplemental oxygen required, laboratory biomarkers such as absolute lymphocyte count, ferritin, LDH, and d-dimer, renal and liver function tests, concomitant medications, past medical history, and results of the chest imaging. After study initiation, chart reviews will be conducted on a daily basis to assess vital signs, changes to concomitant medications, lab values, and oxygenation indices. Study-specific biomarkers: absolute lymphocyte count, serum ferritin, d-dimer and LDH will be measured at Day 3, 7 and 14 following study initiation, unless already checked clinically in the 24 hours prior to the testing time.

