8.3 Laboratory parameters

The following laboratory parameters will be obtained for our study: CBC (total WBCs, Hb, Platelets), absolute lymphocyte count, AST, ALT, serum creatinine, LDH, ferritin and d-dimer. These labs will be obtained at baseline (within 24 hours of study drug initiation) and at days 3, 7 and 14. In case these labs were drawn in the 24 hours prior to the study stipulated time on

clinical grounds, then we will use those values for the study. If not drawn clinically in the preceding 24 hours, then we will obtain these values as research tests. If COVID-19 biorepository sample obtained on the day of these tests, they can be postponed to the next day. In case a subject is discharged from the hospital prior to the 14-day period or is withdrawn from the study, we will make all efforts to perform the Day 14 assessments on that day.

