14.3.4 Adverse events associated with laboratory testing

The following table highlights the laboratory values that are being obtained as part of the study along with the reference range for normal values. While any value outside the reference range will be classified as abnormal, the clinical significance of those abnormal values will be determined based on the criteria set forth in the table. All lab values identified as clinically significant will be marked as an AE. The causality and attribution of the lab value to the study drug, as well as action items with regards to follow-up and management of laboratory values that are listed as clinically significant, will be adjudicated on an individual basis by the study PI.

Laboratory parameter	Reference Range	Reported as clinically significant if
Serum Creatinine	0.50 – 0.99 mg/dl	≥1.5 times baseline
AST	10 – 35 U/L	≥ 105 U/L (3 times ULN)
ALT	6 – 29 U/L	≥ 87 U/L (3 times ULN)
Hemoglobin	11.7 – 15.5 gm/dl	Decrease of ≥2gm/dL from baseline
Total white blood cells	3.8 – 10.8 x 10 ³ /µL	≤ 3 or ≥ 11.5 x 10 ³ /µL
Absolute neutrophils	1500 – 7800 cells/µL	< 1,000 or > 9,500 cells/µL
Absolute lymphocytes	850 – 3900 cells/µL	< 500 or > 4500 cells/µL
Absolute monocytes	200 – 950 cells/µL	< 150 or > 1,500 cells/µL
Absolute eosinophils	15 – 500 cells/µL	< 5 or > 1,000 cells/µL
Absolute basophils	0 – 200 cells/µL	> 500 cells/µL
Platelet count	140 – 400 x 10 ³ /µL	< 120 or > 450 x 10 ³ /µL

Abbreviations: AST = Aspartate aminotransferase, ALT = Alanine aminotransferase, MCH = Mean corpuscular hemoglobin, MCHC = Mean corpuscular hemoglobin concentration, MCV = Mean corpuscular volume, RDW = Red blood cell distribution width.

While the guidance above is meant to cover all laboratory values obtained during the study, we realize that it may not be able to cover all the unique circumstances that can arise during the conduct of a clinical trial. As such, in rare situations, the study PI may change the clinical significance of a lab value outside of the above guidance. We do not anticipate this situation to arise commonly, however, and if deviating from the above range while assigning clinical significance, the reason for this diversion will be clearly outlined in the subject's study binder. Adverse events related to study medication will be tabulated by body system and by severity using the NCI CTCAE v 5.0.

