14.11.1 Registration

Registration of participants on this protocol will employ an interactive data system in which the clinical site (University of Cincinnati) will attest to the participant's eligibility as per protocol criteria and obtain appropriate informed consent. IRB approval for the protocol must be obtained before accrual can occur from the clinical site.

Each participant enrolled will be assigned a local identifier by the enrollment site. This number can be a combination of the site identifier (location code) and a serial accession number. Only the registering site will have access to the linkage between this number and the personal identifier of the subject.

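### The d-dimer limb of the any-one-of-four entry criterion is printed as at least 1 ug/L, which under stated assumptions about normal values does not select for elevated d-dimer; value and unit need reconciling

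*Combined protocol and SAP*

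**What the plan says.** Section 5.2 of the protocol requires, besides confirmed pneumonia and hypoxia, "Presence of at least one additional biomarker that has been shown to predict poor prognosis". Four limbs follow, joined by *or*: ferritin of at least 500 ug/L, LDH of at least 250 U/L, a d-dimer limb, and an absolute lymphocyte count below 1,000/uL. The d-dimer limb reads "c) d-dimer $\geq 1\text{ug/L". The synopsis prints the same value and unit.

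Section 3.2 gives the intent: "Key prognostic biomarkers reported thus far include elevated serum levels of ferritin, d-dimer, LDH, and lymphopenia". It adds: "Lymphopenia has been observed in 60-80% of the hospitalized COVID-19 patients".

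Under Section 14.11.1 the site attests to the participant's "eligibility as per protocol criteria", so the printed threshold is the governing one as far as the documents show.

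Baseline data include "laboratory biomarkers such as absolute lymphocyte count, ferritin, LDH, and d-dimer" (Section 6.1). On timing, Section 8.3 says: "These labs will be obtained at baseline (within 24 hours of study drug initiation) and at days 3, 7 and 14".

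Section 15 and the SAP cite the biomarker requirement when they move from the 40% progression rate in the cited cohort to an expected 50% in the control group.

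**The concern.** The criterion is meant to pick patients with a marker of poor prognosis, and for d-dimer that means a raised level. A cut-off of 1 ug/L appears far below any plausible upper limit of normal, which suggests that value and unit do not belong together. Since any one limb is enough, a limb that nearly everyone meets makes the other three irrelevant, and the whole biomarker requirement ceases to restrict entry.

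What is at stake is who is enrolled, and the enrichment that the sample-size text relies on. Monitoring would not catch the problem: Section 14.11.3 has eligibility reviewed for all screened subjects, but that review is against the printed criteria.

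**Working it through.** **1. Can the documents settle the unit?** No.
- Section 5.2 and the synopsis agree with each other, so neither corrects the other.
- The Section 14.3.4 table is introduced as listing the study's laboratory values "along with the reference range for normal values", but has no row for d-dimer, LDH or ferritin.
- Section 4.3 lists normalization of d-dimer as a key secondary endpoint without a normal limit.
- The eligibility form is not in the documents.

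**2. Printed cut-off against an assumed normal limit.** Assumptions, not in the documents: the upper limit of normal (ULN) lies somewhere from 20 to 1000 ug/L, and normal values generally exceed 1 ug/L. The ratio is 1/ULN:

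| Assumed ULN (ug/L) | Printed cut-off as share of ULN |
|---|---|
| 20 | 1/20 = 5% |
| 100 | 1/100 = 1% |
| 200 | 1/200 = 0.5% |
| 500 | 1/500 = 0.2% |
| 1000 | 1/1000 = 0.1% |

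The cut-off reaches the normal limit only when 1/ULN is at least 1, that is, when the ULN is 1 ug/L or lower. That is 20-fold below the lowest value in the table.

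**3. Effect on the whole criterion.** The criterion is met if ferritin *or* LDH *or* d-dimer *or* lymphocyte count qualifies. If practically every patient meets the d-dimer limb, practically every patient meets the criterion. Under the assumptions in step 2, a hypoxic patient with no abnormal marker meets it.

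**4. How many patients could this reach?** Only those who meet none of the other three limbs and whose d-dimer is below the intended threshold. The documents bound one part of this:
- Lymphopenia in 60-80% leaves 100% - 80% = 20% to 100% - 60% = 40% without it.
- On 30 patients that is 0.20 x 30 = 6 to 0.40 x 30 = 12.

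This is a loose ceiling and not an estimate. Patients who qualify on ferritin, LDH or a truly raised d-dimer must be subtracted, and the documents give no figure for them. The ceiling also assumes that the lymphopenia figure carries over to oxygen-requiring patients and to the 1,000/uL cut-off. Section 3.2 says that lymphocyte counts fall with severity, so the share without lymphopenia may be smaller here. The cut-off behind the 60-80% is not stated, which could move it either way.

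**5. Link to the sample size.** The plan's inputs reproduce: 165/201 = 82.1% and 67/165 = 40.6%, against the stated 82% and 40%. To see whether the unit decides the step to 50%, suppose a working criterion removed a share q of such patients and none of those removed would have progressed, which is the most favourable case for enrichment. The rate among the rest is 0.406/(1 - q). Setting this to 0.50 gives q = 1 - 0.406/0.50 = 0.188. Even in that extreme case about 19% would have to be excluded. The documents do not say what share a working criterion would exclude, so correcting the unit does not by itself justify or refute the 50%.

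**The case against.** The strongest reply is that the documents do not contradict themselves: the same value and unit appear twice, and no passage states another. The defect rests on a normal range from outside the documents. That is correct, and the conclusion is therefore conditional. The condition is not delicate, however, since it fails only if the upper limit of normal is 1 ug/L or lower.

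A character may also have been misread when the PDF was converted to text. Identical printings in two places make this unlikely but do not exclude it, since one may have been copied from the other. The site may in practice have used another unit. Both possibilities stand, and either would reduce the fix to a clerical correction.

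It is also fair to say that no calculation in the plan is wrong. This is a question of an eligibility threshold or its unit, not of arithmetic.

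Three stronger readings are tempting, and the documents support none of them:
- *That a stated number of patients enter wrongly.* The 6 to 12 of 30 is only a ceiling, and the share with no other qualifying marker is nowhere given.
- *That the study loses power.* The plan states no power, and any computed loss would have to assume that the criterion produces no enrichment at all, which does not follow from the unit.
- *That the treatment comparison is biased.* Both arms are randomized from the same admitted population, so it is not.

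**Conclusion.** The point holds in conditional form. With an upper limit of normal anywhere from 20 to 1000 ug/L and normal values generally above 1 ug/L, the printed d-dimer cut-off is 5% to 0.1% of that limit. It then fails to select for the raised marker that Sections 3.2 and 5.2 describe, and the alternatives structure carries that failure to the whole biomarker criterion.

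The consequence is confined to the population admitted and to the enrichment cited in Section 15. Its size is an unknown part of the 20-40% without lymphopenia, subject to the carry-over assumptions in the working. Whether 50% is otherwise a sound control rate is a separate question.

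This should be fixed because it is an operative entry rule and nothing elsewhere in the documents cures it. Confidence is moderate, given the outside assumption and the unseen eligibility form.

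**What to change.** Reconcile the d-dimer value and unit with the basis for the threshold and with the laboratory's reporting unit. State the same value and unit in the synopsis, in Section 5.2 and on the eligibility form. No value is proposed here.

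If patients were enrolled under the printed text, report by arm how many met none of the other three limbs *and* had a baseline d-dimer below the reconciled cut-off. Counting everyone who qualified on d-dimer alone would mix properly eligible patients with affected ones. The baseline values needed are already collected under Sections 6.1 and 8.3. The intent-to-treat primary analysis stays as it is.

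The cost is a one-line amendment in two places, a check of the eligibility form and one row in the baseline table. The downside is that patients who qualify only on the printed value become ineligible, so slightly more screening may be needed to reach 30. How much more cannot be derived from the documents.
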